STUDY TITLE:

Evaluating a Digital Intervention for Binge Eating and Weight Management among Adults with Food Insecurity

PRINCIPAL INVESTIGATOR:

[name]
Department of Medical Social Sciences

VERSION DATE:

June 14, 2024

Indicate Vulnerable Population(s) to be Enrolled	 Children  Cognitively Impaired Adults  Pregnant Women (IF the research activities will affect the pregnancy or the fetus)  Prisoners (or other detained/paroled individuals)
International Research (check this box if you will collect data from individuals located outside the United States)	
Research involving external collaborators (some research activities will be carried out by individuals not employed by Northwestern or NU affiliates)	
Research has U.S. Federal government funding (e.g., NIH, NSF, other federal agencies/departments)	 This is funded by the American Diabetes Association to a NIH-funded P30 Center at Northwestern University & the University of Chicago, who administers the pilot award to the study PI

1.0 Purpose of the study:

The purpose of this study is to (1) adapt the mobile intervention, FoodSteps, to address food insecurity (i.e., tailor the intervention, offer financial support for accessing food to facilitate implementing healthy behavior changes), and (2) test its feasibility, acceptability, and preliminary efficacy to inform a future R01 clinical trial of FoodSteps among this subpopulation. The Specific Aims are to:

Aim 1: Determine the feasibility of delivering the FoodSteps intervention among adults with food insecurity, recurrent binge eating, and diabetes. Feasibility will be based on study recruitment and retention rates, retention to treatment, and adherence documenting prescribed intervention strategies.

Aim 2: Assess the acceptability of FoodSteps by applying user-centered design methodology via qualitative interviews and self-report surveys, which will inform future intervention enhancements.

Aim 3. Derive estimates of the preliminary efficacy of FoodSteps on changes in weight and binge eating from baseline to post-intervention. Efficacy estimates will be used to power a future R01 trial.

Background / Literature Review / Rationale for the study:

Two in five U.S. adults have obesity,¹ which is associated with morbidity, mortality, and high healthcare costs.²⁻⁴ Up to 30% of adults with obesity engage in binge eating,⁵ an eating disorder behavior characterized by eating a large amount of food and experiencing a loss of control while eating.⁶ Binge eating causes excess weight gain, undermines weight control treatment outcomes, and confers risk for comorbidities including metabolic syndrome.^{7,8} Despite their substantial overlap and tendency to persist in the absence of treatment, no intervention sufficiently addresses both obesity and binge eating,⁹⁻¹¹ which results in a pressing clinical gap.

To fill these gaps, we created FoodSteps, the first intervention for both obesity and binge eating, delivered by mobile device to increase scalability. In the first trial of FoodSteps (K01 DK116925; PI [name]), we rigorously designed the intervention with user input and tested its feasibility. Preliminary findings show that FoodSteps is engaging with high rates of completion and adherence, unlike most apps.¹² But, FoodSteps has not been adapted for nor tested among a subpopulation of people with binge eating, obesity, and food insecurity.

Food insecurity, defined as inadequate/inconsistent access to food required for a healthy life,¹³ is increasingly being linked to binge eating.¹⁴ Only 9 people (15%) who enrolled in the K01 clinical trial reported having food insecurity, as recruitment was not designed to target this subpopulation. To inform a future R01 clinical trial of FoodSteps among people with food insecurity, we need to pilot test this intervention among a larger sample. Additionally, FoodSteps has not been tested in people with weight-related health problems such as type 2

diabetes mellitus, a clinically important extension given the prevalence (up to 20%) and negative impact of binge eating among people with diabetes.^{15,16}

Therefore, the overarching goal of this study is to conduct a pilot test of the FoodSteps intervention among adults with recurrent binge eating, Type 2 diabetes, and food insecurity to determine its feasibility, acceptability, and preliminary efficacy among this population.

2.0 Enrollment Criteria:

Participants will be non-pregnant, English-speaking adults age ≥ 18 years with recurrent binge eating (≥ 12 episodes in the past 3 months), type 2 diabetes (self-reported as a current diagnosis), and food insecurity (≥ 2 on the 6-item Short Form Food Security Survey Screener). Individuals will be eligible if they indicate they want to lose weight, are willing to use a mobile application (“app”), and have a Smartphone with Internet access. Participants will also need to have sufficient capacity for calls and text messaging through their cellular carrier plan, have a valid e-mail address so that they can receive study information, and complete relevant study procedures (e.g., consent form, REDCap link with questionnaires), and have a valid five-digit zip code.

Participants will be excluded if they self-report a diagnosis for which the study/intervention is not clinically indicated (e.g., psychosis, mania, dissociation, cognitive impairment). Participants may be excluded if they are currently working with a clinical professional to receive services for management of weight/binge eating or started/recently changed dosage of a medication for binge eating, weight loss, or diabetes.

3.0 Sample Size:

Up to 40 participants will be enrolled in the study.

4.0 Recruitment and Screening Methods:

Recruitment Methods: Participants will be recruited from clinics at Northwestern University (e.g., Center for Lifestyle Medicine) and the University of Chicago (e.g., Eating Disorders Program, Center for Surgical Treatment of Obesity) and the community via flyers (e.g. WIC clinics, IDHS offices offering SNAP applications or mental health services, Greater Chicago Food Depository food pantries), media (including online social media such as Facebook, Instagram, Reddit, and Craigslist), newsletters, referrals, and word of mouth. We also will recruit participants using ResearchMatch and The New Normal, which are free participant recruitment online platforms that are accessible to researchers at participating institutions including Northwestern University, and Northwestern’s StudyTracker. Additionally, we will recruit potentially eligible participants who have filled out an eligibility screener for a concurrent study and who have consented to having their screener data shared with other approved research projects by the PI. Across all recruitment pathways, information/study advertising content will remain consistent with

IRB-approved recruitment language.

Screening Methods: Interested individuals will complete an online screener survey administered via REDCap to assess for potential eligibility. The online screener will include questions about the individual's contact information, demographics, food security status, smartphone ownership, access to a scale, current treatment utilization, mental and physical health concerns (e.g., type 2 diabetes), and interest/capacity to participate in study activities. Interested individuals also will be asked to self-report their height, weight, and number of episodes of binge eating over the past 3 months. "Helper text" may be added in REDCap to questions that appear challenging to understand to improve reading comprehension.

Individuals recruited from the concurrent study will complete a shortened screener via REDCap which will only include questions about the individual's food security status (i.e., items not assessed on the other study's screener); these individuals' responses to the other items from the concurrent study's eligibility screener will be copied to this study's REDCap.

Potentially eligible individuals will then be invited to complete an assessment to confirm eligibility. This assessment will occur via videoconference or telephone call (e.g., via Zoom, CiscoJabber). First, participants will complete informed consent. Consenting individuals then will complete the assessment, which will include a semi-structured interview with a trained assessor to assess for the number of binge episodes over the past three months and other eating disorder pathology. Individuals will also be asked to complete surveys, which will be sent as a REDCap link via email. Questionnaires will assess participants' demographics not captured at screening (e.g., marital status, education level, employment status, income, insurance), height, weight, eating-related symptoms, food security, and mood. Participants can skip any questions as a part of the interviews or questionnaires and can stop their participation at any time. "Helper text" may be added in REDCap to questions that appear challenging to understand to improve reading comprehension.

Of those eligible, participants will be selected with a range of backgrounds to ensure a diverse and representative sample of target users. Ineligible individuals will be offered referral information for treatment.

5.0 Research Locations:

Research procedures will occur at the Center for Behavioral Intervention Technologies (CBITs) lab space at Northwestern University and/or remotely (e.g., via Zoom, telephone, CiscoJabber). CBITs has private offices and a usability lab.

6.0 Multi-site Research (research that involves external collaborating institutions and individuals):

NA

7.0 International Research (where data collection will occur outside the United States and U.S. territories)

NA

8.0 Procedures Involved:

Please check the boxes for all applicable data collection procedures you plan to use:

- One-on-one interviews
- Focus Groups
- Questionnaires/surveys
- Analysis of secondary data (medical record data, educational records, government or private sector datasets, etc.)
- Ethnographic observation
- Physiological measurements (e.g., EEG, EKG, MRI)
- Biospecimen collection (saliva samples, blood draws, hair samples, etc.)
- Mobile applications/data collection devices (e.g., Fitbits, actigraphs, etc.)
- Behavioral decision-making tasks (e.g., puzzles, interactive games, etc.)
- Physical activities such as walking and other forms of exercise
- Other procedures (briefly list types of procedures here if not covered by the check-boxes above): Measure height and weight

Eligible individuals will be invited to enroll in the pilot trial. Participants who elect to enroll will be sent an electronic scale and will schedule an onboarding call. This call will occur by telephone or an internet-based phone service (e.g., Google Hangouts/Voice, CiscoJabber, Zoom). During the onboarding call, enrolled participants will provide their weight using the electronic scale and onboard to the FoodSteps intervention. Participants will keep the electronic scale from onboarding for use throughout the remainder of the study; they will be allowed to keep the scale after the study ends. Within one month of participants discontinuing or completing the 16-week trial, we will alert the electronic scale contractor (BodyTrace) to request termination of data transmissions from the participant's scale to the research team. Each enrolled participant will also receive a stipend of \$10 per week (up to \$160 total) to support implementing healthy behavior changes during the intervention. The stipend will be prorated and given to participants at the beginning of every week of the intervention. If a participant chooses to withdraw from the intervention before the end of the study, they will not continue to receive the stipend. Additionally, to sustain participant engagement over the 16-week study, enrolled participants may be sent variable promotional, study-branded materials—and not extra compensation—such as a tote bag, sticker, and/or water bottle (valued at ~\$2-20) during the study period.

Intervention: Enrolled participants will be offered access to the mobile intervention, FoodSteps, with coaching for 16 weeks. All participants will receive the intervention; there is no inactive control. The intervention is focused on addressing binge eating and weight management, with recommended weekly modules for participants to complete. Participants will access the intervention by creating a personal password known only to the participant. FoodSteps can be accessed as a website app on a smartphone or on a computer or tablet.

Participants can choose to use or not use the intervention and still be enrolled in the study. The intervention and data are hosted on a secure, encrypted server. The information that participants enter into the intervention will not include anything that can identify them except for their email address, phone number, and zip code.

Coaching: Each participant will be assigned a coach, who is trained and supervised weekly by a clinical psychologist. Coaching follows a low-intensity model aimed at encouraging participants to use the intervention and practice skills in their daily lives, as well as provide some technical support as needed. Coaches will use messaging such as text or e-mail to communicate with participants through a password-protected website on a secure server. Coaching will begin with an initial ~30-minute phone call to establish goals and build rapport, ensure the participant can access the intervention, set expectations for the coach-participant relationship, and make the participant aware that they can request treatment referral information any time as well as explain how to navigate to the intervention's Resources page which includes treatment referral information. Thereafter, participants will receive ~1-2 messages per week from their coach to offer encouragement, reinforce app use, and check-in on progress or challenges. Coaches also will aim to respond to participant-initiated messages within 1 working business day. An optional ~10-minute call at week 8 (mid-way through the intervention) will be offered to participants to check in on their progress, with potential for additional calls as needed. After participants schedule their coaching call, they may receive emails and/or text messages (up to 4) reminding them of their upcoming appointment. Participants who have already consented into the study will not receive text message reminders.

Study assessments will occur again at mid-intervention (8-weeks) and post-intervention (16-weeks). Baseline (i.e., the eligibility assessment), mid-intervention, and post-intervention assessments will include interviews and/or questionnaires. After participants schedule their research assessments, they may receive emails and/or text messages (up to 4) reminding them of their upcoming appointment. Participants who have already consented into the study will not receive text message reminders. Interviews and questionnaires will assess the following topics: personal and demographic information, treatment and stipend utilization, height, weight, number of binge episodes over the past three months, eating-related symptoms, stress, shame, food security, and experiences with technology. The following questionnaires will be administered via a

REDCap survey link:

Measure	Timepoint		
	Baseline	Mid-intervention	Post-intervention
Demographic Information	X		
Eating Questionnaire	X	X	X
Stipend Questionnaire			X
CIA 3.0	X	X	X
CESDR-10	X	X	X
6-item FI Screener		X	X
System Usability Scale		X	X
Treatment Utilization		X	X
Perceived Stress Scale	X	X	X
Personal Feelings Questionnaire	X	X	X
Implementation Questionnaire (Baseline)	X		
Implementation Questionnaire (Post-Intervention)			X

Intervention use data (from start of intervention through 16-week post-intervention) and weights from the electronic scale also will be automatically collected.

Interviews will be conducted via Zoom video call or telephone by a trained assessor and questionnaires will be e-mailed as a REDCap survey link to participants. Height and weight will be self-reported as a part of the questionnaires; at mid-intervention and post-intervention, participants also will be asked to provide a weight using their electronic scale. Participants can choose not to answer any questions as a part of the interviews or questionnaires and can stop the assessments at any time. “Helper text” may be added in REDCap to questions that appear challenging to understand to improve reading comprehension.

Intervention use data will be downloaded monthly from the intervention and in entirety at the end of the study by an approved research team member. Following the study, all intervention use data will be removed from the intervention host server.

All data will be stored in FSM research files on password protected computers on secure servers, or within the Research Electronic Data Capture (REDCap)

program on a HIPAA-compliant server with secure access for approved study staff.

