9.0 Research with Vulnerable Populations

NA

10.0 Incomplete Disclosure or Deception:

NA

11.0 Consent Process:

Screening: Interested individuals will complete an online consent form prior to beginning the online screening survey or the shortened screening survey. The online consent form will describe the online screening survey in REDCap.

Eligible individuals who are invited to participate in the eligibility assessment will be asked to complete an online consent form via REDCap prior to beginning the assessment. A PDF copy of the consent form will be emailed to participants prior to the assessment so they can review the form in advance. Then during the assessment, an approved member of the research team will explain the study and procedures, and participants will be allowed as long as needed to review the consent form and ask any questions they may have. The assessor will then provide the participant with the REDCap link so the participant can e-sign the form. Individuals who do not consent to study procedures will be unable to participate.

12.0 Waiver of Participant Signature on Consent Form:

N/A

13.0 Waivers and Alterations of Consent Information:

NA

14.0 Financial Compensation:

Compensation will be prorated in the study. Participants will receive increasing amounts for each assessment they complete: \$20 for baseline (eligibility), \$25 for mid-intervention (8-weeks), and \$30 for post-intervention (16-weeks). To encourage participants to complete all assessments, they can earn an additional \$15 for completing all assessments. This means participants have potential to be compensated \$90 total for completing all study activities. Hyperwallet electronic gift cards (e-gift cards) will be provided to participants. Hyperwallet e-gift cards may be used anywhere Visa is accepted. Participants also will be allowed to keep their electronic scale. Participants will not be compensated for completing the intervention or communicating with their coach.

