1.0 Audio/Video Recording/Photography

Interview assessments will be audio and/or video recorded to assess reliability of assessors in administration or for subsequent qualitative analyses.

After each session, audio and/or video files will be transcribed (e.g., automatically by Zoom, manually by an approved research member) and the recordings and transcriptions will be uploaded to the FSM research files and removed from the recording device. Additional edits may be made to the transcription files by an approved research team member. All transcripts of the recordings will be de-identified. Recordings and transcripts will be stored on password protected computers and secure servers only accessible to approved study staff.

15.0 Potential Benefits to Participants:

Participants may experience reductions in weight and binge eating, as well as improvements in core psychopathology (i.e., overvaluation of weight and shape, unhealthy weight control practices, and negative affect). These changes have potential to reduce the onset or maintenance of medical problems and total health care service use and costs associated with obesity and binge eating. Participants may also benefit from knowing that their use of the intervention and feedback will help inform improvements to the intervention that may improve the precision and efficacy of care for individuals with obesity and binge eating. All participants will be provided with referral information for treatment following the trial.

16.0 Risks to Participants:

There are minimal risks associated with participating in the study. Potential risks that might exist fall into the following four categories: (a) risks associated with the intervention; (b) risks associated with study assessments; (c) risks associated with potential loss of confidentiality; and (d) risks of worsening symptoms.

- (a) Risks associated with the intervention: Digital mental and behavioral health interventions have not been shown to cause any harm. All intervention activities are optional, and participants can discontinue using the intervention at any time, while still participating in the study.

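### Does stopping the weekly stipend on withdrawal, but not on silent non-use, spoil retention to treatment as a feasibility measure?

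*Protocol*

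**What the plan says.** Section 1.0 describes the adaptation of FoodSteps as including a plan to "offer financial support for accessing food to facilitate implementing healthy behavior changes". Aim 1, in the same section, sets the outcomes: "Feasibility will be based on study recruitment and retention rates, retention to treatment, and adherence documenting prescribed intervention strategies". Neither Aim 1 nor any later section gives an operational definition of, or a threshold for, retention to treatment.

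Section 8.0 sets the payment: "Each enrolled participant will also receive a stipend of \$10 per week (up to \$160 total) to support implementing healthy behavior changes during the intervention". On timing: "The stipend will be prorated and given to participants at the beginning of every week of the intervention". On leaving: "If a participant chooses to withdraw from the intervention before the end of the study, they will not continue to receive the stipend". The same section separates use from enrolment: "Participants can choose to use or not use the intervention and still be enrolled in the study". Section 16.0, item (a), says much the same of stopping part-way: "participants can discontinue using the intervention at any time, while still participating in the study".

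Section 14.0 covers assessment payments, which are separate from the stipend, and states: "Participants will not be compensated for completing the intervention or communicating with their coach".

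Section 8.0 also provides for automatic collection of intervention use data from the start through week 16, monthly download of those data, treatment-utilization questionnaires at weeks 8 and 16, and a stipend questionnaire at week 16. Section 18.0 requires information to be documented on each participant who drops out.

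**The concern.** Two people can leave the treatment in the same practical sense, by no longer using FoodSteps, and be treated differently. The one who says so loses the remaining weekly payments; the one who says nothing seems to keep them. Everyone in the trial is food-insecure by eligibility, so the money matters, and there is a reason not to declare withdrawal.

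If retention to treatment meant not having formally withdrawn, the rate could stay high while use fell away. A pilot meant to inform a larger trial might then report good retention for an app that many participants had stopped opening. The statement in Section 14.0 that completing the intervention is not compensated can also look at odds with a stipend that ends on withdrawal.

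**Working it through.** **Payment figures.** Inputs are from Sections 8.0 and 14.0.

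- Maximum stipend: 16 × 10 = 160 dollars, which reproduces the stated maximum.
- Assessment payments: 20 + 25 + 30 + 15 = 90 dollars, which reproduces the stated total.
- Ratio: 160 / 90 = 1.8.
- Stipend forfeited by withdrawing after week w: 10 × (16 − w). This gives 150 dollars at w = 1, 120 at w = 4, 80 at w = 8 and 40 at w = 12.
- Stipend forfeited by stopping use without declaring it: 0 dollars. This is inferred, because payment goes to each enrolled participant and enrolment does not depend on use; the protocol does not say it outright.

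So the incentive exists, and its maximum is larger than all assessment pay together.

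**Effect on a retention rate.** Let N be the number enrolled, W the declared withdrawals and S the silent non-users.

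- Retention by declared status: (N − W) / N.
- Retention by logged use: (N − W − S) / N.
- Difference: S / N.

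N = 40 is the maximum in Section 3.0. The protocol gives no values for W or S, so the following are assumptions. With W = 4, status-based retention is 36/40 = 90% (exact 95% CI 76% to 97%).

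| Silent non-users S | Use-based retention | Exact 95% CI | Difference |
|---|---|---|---|
| 0 | 36/40 = 90% | 76% to 97% | 0 points |
| 4 | 32/40 = 80% | 64% to 91% | 10 points |
| 8 | 28/40 = 70% | 53% to 83% | 20 points |
| 12 | 24/40 = 60% | 43% to 75% | 30 points |

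The difference is whatever S is assumed to be, divided by 40. The table shows how the mechanism scales; it is no evidence that a gap will occur. The gap is zero if nobody stops silently, or if retention is counted from use.

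**Which count does the protocol prescribe?** Neither.

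- Aim 1 names the measure and stops there.
- Withdrawal is not the only way out of treatment that the protocol recognises. Section 16.0 provides for discontinuing use while remaining in the study, and Section 8.0 separates use from enrolment. The text gives no reason to assume a withdrawal-based count.

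**Would silent non-use stay hidden?** No. It would show in the automatic use logs and in adherence, which Aim 1 lists separately. With no threshold attached to retention, that one rate cannot by itself declare the treatment feasible.

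**Does Section 14.0 conflict with Section 8.0?** No. If non-users keep the stipend, it is not a payment for completing the intervention, so the two statements agree.

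**The case for a change.** The strongest case for a change is that the payment rule is fixed in the protocol and acts on the behaviour being measured. No later analysis plan can recover withdrawals that participants had a reason not to declare. Because adherence is already the measure tied to documented use, a status-based reading of retention to treatment is plausible. The protocol also never separates withdrawing from the intervention from discontinuing its use, so who has left treatment is open. Calling the stipend part of the package does not fully answer this: someone who collects it and never opens the app would still count as retained under a status definition, although Aim 1 is about delivering FoodSteps.

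What stands is that the two terms are not distinguished, and that a withdrawal-based rate would be conditional on the stipend and could overstate use. But undeclared withdrawals need not be recovered when use itself is logged for everyone, because the analyst can simply count from the logs. Ending one component when a person leaves the package is ordinary. It limits generalisation to FoodSteps without a stipend, but it is not a bias in a pilot of FoodSteps with one.

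The alternative of paying the stipend through week 16 to all who remain in the study brings no clear gain. It would alter a declared component and move the incentive onto study retention, which is another Aim 1 measure. A status-based count would still miss silent non-use.

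**Conclusion.** No change to the plan is needed. The asymmetry is real: up to 150 dollars lost by declaring withdrawal after week 1, against apparently nothing for silent non-use. It distorts retention to treatment only under a definition that the protocol does not adopt, and then by S / N, which cannot be computed from the documents.

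What remains is an undefined measure of the kind often left to the analysis plan. The data to fill it sensibly are already collected: retention counted from logged use, formal withdrawals listed separately, and the stipend noted as part of what was delivered.

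This conclusion assumes that the use logs are complete for all enrolled participants, and that the report shows adherence alongside retention, as Aim 1 implies. If a final report gave only a withdrawal-based rate and presented it as evidence of continued use, the criticism would apply to that report.

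### Does the blank Baseline cell for the 6-item FI Screener leave the study without a usable starting value for food security?

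*Protocol*

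**What the plan says.** Section 2.0 of the Protocol makes food insecurity an entry criterion, set at a score of 2 or more on a 6-item short form.

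Section 4.0 describes two steps before enrolment.

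- The first is an online screener, whose topics include "food security status, smartphone ownership, access to a scale, current treatment utilization". People who come from the concurrent study instead "complete a shortened screener via REDCap which will only include questions about" food security, because their other answers are carried over.
- In the second, potentially eligible people are "invited to complete an assessment to confirm eligibility". After consent they have an interview and receive REDCap questionnaires. The topics listed for these are "demographics not captured at screening" and then "height, weight, eating-related symptoms, food security, and mood".

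Section 8.0 ties the second step to the study timepoints: "Baseline (i.e., the eligibility assessment), mid-intervention, and post-intervention assessments will include interviews and/or questionnaires". The table that follows gives the schedule of REDCap forms. Its row for the "6-item FI Screener" is blank at Baseline and marked at mid-intervention and post-intervention. No other row is named as a food security form.

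**The concern.** Read together, sections 4.0 and 8.0 give different accounts of what is collected at Baseline. Staff who build the Baseline survey from the table would leave the food security form out; staff who work from section 4.0 would put food security items in. A value that is not collected before treatment cannot be recovered later.

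The point draws attention because food insecurity defines the population, the intervention is adapted to it, and the same form is repeated at weeks 8 and 16 with no control group. If the table is followed, the only named pre-intervention score is the one used to select participants. A change described from that score would be open to regression to the mean, and the protocol does not fix the interval between screening and the start of the intervention.

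**Working it through.** No formula applies and the protocol gives no figure to reproduce. The check compares the two places line by line.

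**Section 4.0 topics against the Baseline column of the section 8.0 table**

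| Topic at the eligibility assessment | Matching form | Baseline mark |
|---|---|---|
| Demographics | Demographic Information | Yes |
| Height, weight | No row of their own | Not applicable |
| Eating-related symptoms | Eating Questionnaire, CIA 3.0 | Yes |
| Food security | 6-item FI Screener | No |
| Mood | CESDR-10 | Yes |

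Height and weight have no row because, as section 8.0 explains, "Height and weight will be self-reported as a part of the questionnaires". Food security is therefore the one listed topic whose matching form is not scheduled at Baseline. The mismatch is real.

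**Pattern of the table.** It has 12 rows. Eight forms are marked at both week 8 and week 16: Eating Questionnaire, CIA 3.0, CESDR-10, 6-item FI Screener, System Usability Scale, Treatment Utilization, Perceived Stress Scale and Personal Feelings Questionnaire. Five of the eight have a Baseline mark, and 8 − 5 = 3 do not: the 6-item FI Screener, the System Usability Scale and Treatment Utilization.

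The three blanks can be explained:

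- The System Usability Scale cannot be answered before the app has been used.
- Treatment utilization and food security are both asked in the online screener.

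So the table is consistent with a simple rule: a topic already asked at screening is not asked again at Baseline.

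**Is a pre-intervention value missing under either reading?**

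- If the table is right, the value comes from screening. The full screener and the shortened screener both ask about food security.
- If section 4.0 is right, there is a second value at the eligibility assessment.
- Under both, the entry criterion in section 2.0 cannot be applied without a score on the 6-item form. Every enrolled participant must therefore have one before the intervention starts.

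**Does any planned result use it?** Aim 1 rests on recruitment, retention and adherence. Aim 2 rests on interviews and self-report surveys of acceptability. Aim 3 estimates change in weight and binge eating. None uses a change in food security.

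**The case for a change.** The strongest case for acting is that screening explains the table but not section 4.0. That section names food security twice, once for the screener and again for the eligibility assessment. Where the authors meant to avoid repeating screener items they said so, as they did for demographics, and they attached no such limit to food security. Height and weight are also asked at both steps, so repetition is not foreign to the design. Treatment utilization does not appear in the list for the eligibility assessment, so its blank cell contradicts nothing. The remedy would also be cheap: one table cell, or one edited sentence.

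This establishes that the two places do not match. It does not show that the table is the one in error.

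- Section 4.0 gives topics, not an inventory of forms. It omits stress, shame and implementation, although the Perceived Stress Scale, the Personal Feelings Questionnaire and the baseline Implementation Questionnaire all carry a Baseline mark.
- It names food security as a topic and does not name the 6-item form. The items could sit inside another baseline form whose content is not shown, as height and weight do.

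The regression-to-the-mean argument is sound in principle, but it is aimed at an analysis the protocol does not propose. Adding the form at Baseline might not cure it either: that visit is held to confirm eligibility, and if food security is re-checked there, the new score is a selected score as well.

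**Conclusion.** The inconsistency exists, but it is clerical and calls for no change to the plan. Its extent is one form out of the 8 that are repeated at weeks 8 and 16. Its effect on the stated aims is nil, because none of them uses change in food security. Every participant has a pre-intervention score whichever place is followed. An analyst who wished to describe food security over time would take the screening score as the starting value, or the Baseline score if one was collected, and would say which.

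The conclusion rests on three readings. The form in the table is taken to be the 6-item form named in the entry criterion. The entry score is taken to be kept with the study data, which section 17.0 supports in saying that screener data are retained for research. And no analysis of change in food security is taken to be planned; the protocol describes none. If such a change were later made an outcome, the source and timing of its starting value would have to be stated. The size of any regression to the mean cannot be estimated from the protocol, which gives no mean, standard deviation or retest correlation for the score.
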